3.3. CONCOMITANT MEDICATIONS AND PROCEDURES

3.3.1. Concomitant Medications and Procedures

Concomitant medications are any treatments received by the patient concomitantly with study treatment, from first dose of study treatment to last dose of study treatment + 30 days.

Concomitant medications include all medications used to mitigate AEs such as nausea, for supportive care, to treat or prevent infection, or to maintain the use of dexamethasone in combination of selinexor in this study. All concomitant medication(s) must be reported on the eCRF. Any diagnostic, therapeutic, or surgical procedure performed during the study period should be recorded, including the dates, description of the procedure(s), and any clinical findings, if applicable.

All medications will be coded using the WHO DDE Version March 2017.

Please refer to the Karyopharm Biostatistics and Statistical Programming Rule Book on definitions on prior and post-treatment medications.

3.3.2. Analysis Methods

Concomitant medications will be summarized according to the WHO DDE dictionary using the mITT population, by the anatomic and therapeutic class (ATC) level 2 (therapeutic level) and level 4 (generic level). All ATC codes corresponding to a medication will be summarized, and patients will be counted once in each ATC category linked to the medication. Therefore, patients may be counted several times for the same medication. The summary will be sorted by decreasing frequency in ATC level 2 and then ATC level 4 in the mITT population.

Please refer to Section 2 for details on data handling rules related to computation, dates, imputation for missing dates.

3.4. EXTENT OF STUDY TREATMENT EXPOSURE AND COMPLIANCE

The extent of study treatment exposure and compliance will be summarized in safety population.

3.4.1. Extent of Study Treatment Exposure

The extent of exposure for the study treatment will be assessed using the following variables:

- Duration of study treatment exposure
- Number of selinexor doses received
- Number of dexamethasone dose received
- Number and percentage of patients with a selinexor dose reduction
- Number and percentage of patients with a dexamethasone dose reduction
- Number and percentage of patients with a selinexor dose interruption
- Number and percentage of patients with a dexamethasone dose interruption
- Number and percentage of patients with study treatment discontinued

Duration of study treatment exposure is defined as the date of last study treatment - date of first study treatment + 1, regardless of unplanned intermittent discontinuation.

3.4.2. Compliance

Study treatment compliance will be summarized descriptively as a quantitative variable among the mITT population, calculated as

$$\frac{\text{number of study treatment doses taken}}{\text{number of study treatment doses prescribed}} \times 100.$$

A study treatment dose is considered prescribed if selinexor and/or dexamethasone is prescribed. The number and percentage of patients with study treatment compliance $\geq 70\%$ will be provided. Note that the number of prescribed study treatment doses does not include doses missed due to treatment interruption or other reasons not related to patient choice.

Selinexor compliance is defined similarly among the mITT population as

$$\frac{\text{number of selinexor doses taken}}{\text{number of selinexor doses prescribed}} \times 100.$$

The number and percentage of patients with selinexor compliance $\geq 70\%$ will be provided. Similarly, the number of prescribed selinexor doses does not include doses missed due to treatment interruption or other reasons not related to patient choice. Patients with selinexor compliance $< 70\%$ will be excluded from the PP population.

4. EFFICACY

Patient response at each time point will be assessed centrally by an IRC according to the IMWG response criteria (*Kumar 2016*) for MM. Unless otherwise specified, MM response assessment refers to assessment determined by IRC. The primary endpoint (ORR) is based on these IRC assessed responses in the mITT population.

Documentation of response requires two consecutive readings of the applicable disease parameter (serum M-protein, urine M-protein, serum FLC, or quantitative immunoglobulin level), performed at any time with no minimum interval required between the two readings. The date of response or PD will be assigned to the earlier date of the two independent samples, unless PD is based on an unambiguous criterion such as a new plasmacytoma lesion.

If a patient had one PD assessment but was not subsequently confirmed, unless IRC considers the progression assessment unambiguous, it is not considered a PD (*Kumar 2016*).

Unless otherwise specified, efficacy analyses will use the mITT population. Analyses for the primary efficacy endpoint of ORR and the key secondary efficacy endpoints of DOR, CBR, and duration of clinical benefit will be repeated in the other efficacy populations and additional analysis populations. If relevant, selected efficacy analyses for other efficacy endpoints will be repeated in selected additional analysis populations.

4.1. PRIMARY EFFICACY ENDPOINT

4.1.1. Definition

The primary endpoint is ORR which is defined as the proportion of patients who achieve a confirmed PR or better (i.e., PR, VGPR, CR, or sCR), as assessed by the IRC, during or after the study treatment, before documented disease progression or initiating a new MM treatment.

4.1.2. Primary Analysis of ORR

For the primary analysis of superiority to the minimal threshold ORR, analysis will be performed using the 2-sided, exact 95% confidence interval (CI), calculated for the rate of ORR among the mITT population, and statistical significance will be declared if the lower bound of this interval is greater than 10%.

4.1.3. Supportive Analyses of ORR

CCI

- [REDACTED]
- [REDACTED]
- [REDACTED]
- [REDACTED]
- [REDACTED]
- [REDACTED]
- [REDACTED]

4.2. SECONDARY EFFICACY ENDPOINTS

Several of the secondary efficacy endpoints define durations based on either the progression free survival (PFS) status and time, or time to progression (TTP) status and time. In PFS, death with any cause is considered as an event. In TTP, only death due to disease progression is considered as an event. Please refer to Table 4-1 and Table 4-2 for details on censoring rules for PFS and TTP respectively.

4.2.1. Duration of Response (DOR)

4.2.1.1. Definition

DOR is defined for patients with a confirmed PR or better as the duration from first observation of at least PR to time of IRC-determined PD or death due to disease progression, whichever occurs first. The censoring method for DOR is the same as the censoring method for TTP in Table 4-2.

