4.2.2. Best Overall Response and Clinical Benefit Rate (CBR)

4.2.2.1. Definition

The number and percentage of patients in the individual response categories (MR, PR, VGPR, CR, sCR) based on best response will be calculated respectively.

CBR is defined as the proportion of patients who achieve a confirmed MR or better, i.e., MR, PR, VGPR, CR, sCR. Duration of clinical benefit is defined as the duration from first observation of at least MR to time of IRC-determined PD or death due to disease progression, whichever occurs first. Responders without IRC-determined PD or death due to disease progression will be censored at the censored date for TTP.

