4.2.5. Time to Progression (TTP)

4.2.5.1. Definition

TTP is defined as the duration from start of study treatment to time of IRC-determined PD or death due to disease progression, whichever occurs first. Please refer to Table 4-2 for details on TTP outcome status and date definition. Unless otherwise specified, PD assessment refers to assessment determined by IRC. But for the cause of death, disease progression refers to investigator assessment as specified on the eCRF death report page.

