4.2.5.2. Analysis Methods

Table 4-2 TTP outcome and censoring definition

Situation	Date of event or censoring	Outcome
No adequate post-baseline disease status assessment unless death due to disease progression occurs prior to first post-baseline assessment	Start of study treatment	Censored
Death due to disease progression before IRC-determined PD without a gap of 65 days or longer before death	Death date	TTP event
IRC-determined PD without a gap of 65 days or longer before progression	Date of disease progression	TTP event
No IRC-determined PD or death due to disease progression on or before 
 1. Death due to reasons other than disease progression 2. database cut, 3. withdrawal of informed consent, 4. lost to follow-up, 5. documented treatment discontinuation 6. start of new MM treatment, whichever occurs first 	Date of last adequate disease assessment prior to the earliest occurrence of the events (1. – 6.) listed in the left column	Censored
No IRC-determined PD or death due to disease progression before a gap of 65 days or longer, which corresponds to 2 or more consecutively missed scheduled disease status assessment	Date of last adequate disease assessment prior to the gap	Censored

Median TTP with 95% CI will be estimated based on the Kaplan-Meier method. The Kaplan-Meier curve for TTP will be provided.

The following supportive analyses will be conducted:

- TTP based on Investigator assessment
- TTP in the BCLPD-ref, CLPD-ref, BCPD-ref, and CPD-ref populations respectively, if sufficient data exist
- TTP on most recent prior therapy

Note that MM response assessment is scheduled to be conducted every 28 days. The maximum allowed gap length of 64 days is selected to correspond to 2 scheduled response assessments while allowing small deviations from target dates.

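### The TTP censoring rules reused for DOR and duration of clinical benefit are not limited to the time after first response, so a late responder can be censored before the duration starts

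*SAP*

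**What the plan says.** **Who is a responder.** SAP 4.1.1 counts a confirmed PR or better reached "during or after the study treatment, before documented disease progression or initiating a new MM treatment". It does not exclude a response first seen after missed visits. SAP 4.2.1.2 summarises DOR among all patients with a confirmed PR or better.

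**When DOR starts.** SAP 4.2.1.1 defines it as the "duration from first observation of at least PR to time of IRC-determined PD", or death due to progression if that comes first.

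**How it is censored.** SAP 4.2.1.1 continues: "The censoring method for DOR is the same as the censoring method for TTP in Table 4-2". For duration of clinical benefit, SAP 4.2.2.1 says: "Responders without IRC-determined PD or death due to disease progression will be censored at the censored date for TTP". The introduction to SAP 4.2 says that several secondary endpoints "define durations based on either the progression free survival (PFS) status and time, or time to progression (TTP) status and time".

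**What Table 4-2 does.** It was written for an interval that begins at first dose: "TTP is defined as the duration from start of study treatment to time of IRC-determined PD or death due to disease progression". One row lists six triggers, among them "documented treatment discontinuation", and censors at the last adequate assessment before the earliest of them. The gap row censors at the "Date of last adequate disease assessment prior to the gap". Neither row mentions response. The DOR definition in Protocol 13.3.4 adds only that deaths from other causes are censored.

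**The concern.** A patient can enter the DOR analysis with a first PR that comes after treatment stopped or after a long gap in assessments. For that patient the Table 4-2 trigger has already occurred, so the censoring date can precede the date on which DOR starts. On the natural reading of the gap rows, a progression observed later is discarded as well.

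A Kaplan-Meier analysis has no place for a negative time. Someone would have to drop the patient or invent a rule, and in an open-label single-arm study that would happen once the responses were known. If such patients were dropped, ORR and DOR would describe different sets of responders. SAP section 4 treats DOR and duration of clinical benefit as key secondary endpoints, and SAP 1.6 promises an ORR and DOR update before the marketing application.

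**Working it through.** The documents give no planned figure for DOR (no event count, precision or rate of late response), so there is nothing to reproduce. The check applies the stated rules to constructed records. The study days are assumptions; the rules are the SAP's.

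**Inputs**
- Duration = end date - start date + 1 (SAP 4.2.4.2).
- Response is dated at the earlier of the two confirming samples, with no minimum interval between them (SAP section 4).
- Assessments are every 28 days on treatment (SAP 4.2.5.2). The end-of-treatment visit is up to 14 days after last dose and includes the full marker set. Follow-up is every 3 months, plus or minus 14 days (SAP Table 7-1).
- The gap threshold is 65 days (SAP 1.8 and Table 4-2).

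**Cases where the rule works.** Assessed Days 29, 57, 85 and 113, first PR Day 57, on treatment to Day 120, no PD: 113 - 57 + 1 = 57 days, censored. First PR Day 57, treatment stopped Day 60, confirmed Day 71: censored at Day 57, so 57 - 57 + 1 = 1 day.

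**Example 1: first PR after treatment stop.** SD on Day 29, last dose Day 50, first PR at the end-of-treatment visit on Day 60, confirmed Day 64, no PD. If discontinuation is dated at last dose, the last adequate assessment before it is Day 29. DOR = 29 - 60 + 1 = **-30 days**. Duration of clinical benefit is the same, since Day 60 is also the first MR or better.

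**Example 2: first PR after a gap, then PD.** Assessed Day 29, next Day 99 (PR), confirmed Day 127, then every 28 days to PD on Day 211. The gap is 99 - 29 = 70 days. If any gap before PD disqualifies the event, DOR is censored at Day 29: 29 - 99 + 1 = **-69 days**. The evident intention is 211 - 99 + 1 = **113 days with an event**. This applies to DOR only: SAP 4.2.2.1 censors only responders without PD or progression death, so duration of clinical benefit is 113 days with an event.

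**Example 3: first PR after a gap, no PD.** On treatment to Day 200, assessed Days 29, 113, 141 and 169, first PR (and first MR or better) Day 113. The gap is 113 - 29 = 84 days. Censoring at Day 29 gives 29 - 113 + 1 = **-83 days**. Running the gap rule from first response gives 169 - 113 + 1 = **57 days**, censored.

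**Size per patient.** The Part 1 penta-refractory ORR was 20% (Protocol Table 3) and the Part 2 target is 122 (Protocol synopsis, Study Numbers). 0.20 x 122 = 24.4, or about 24 responders; 1/24 is about 4%.

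**Effect on the median.** Take 3 months as 90 to 92 days from last dose. The first follow-up visit then falls between 90 - 14 - 14 = 62 and 92 + 14 = 106 days after the end-of-treatment visit, so the 65-day rule would usually apply straight after a post-stop response. With the rule run only from first response, Example 1 becomes 64 - 60 + 1 = 5 days, censored. A time censored before the first event is in no risk set when an event occurs, so keeping or dropping it leaves the Kaplan-Meier curve unchanged. A response after a gap, as in Examples 2 and 3, can contribute real follow-up or an event.

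**The case against.** **The DOR text adopts a method, not a date.** Applied to an interval that starts at first PR, the method could be read as running the gap rule only from there. That is a fair reading of 4.2.1.1 and would repair Examples 2 and 3 for DOR. It does not settle the treatment-stop row, which still points to an assessment before the response. It also sits uneasily with SAP 4.2, which refers to TTP status and time, and with 4.2.2.1, which reuses the TTP date itself.

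**Example 1 depends on an undefined date.** The visible SAP does not say that discontinuation is dated at last dose. If it were documented after the Day 60 assessment but before Day 64, the censoring date would be Day 60 and DOR 60 - 60 + 1 = 1 day. This stands, and the example is conditional on it.

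**Example 2 depends on how the gap condition is read.** It could mean only the interval immediately before progression, and Table 4-2 gives no order of precedence between its rows. The reading used is the natural one, not the only one.

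**Nobody is authorised to drop responders.** SAP 4.2.1.1 and 4.2.1.2 cover every confirmed responder, so a negative value would show up as a derivation error. That is true, but the plan does not say how to resolve it.

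**Stronger inferences that the documents do not support.** A reader might infer that median DOR is overstated. Nothing shows that late responders have shorter responses, and early censored times would not normally move the median. A reader might think duration of clinical benefit is worse affected throughout, but for a responder with later PD its wording is the safer of the two. Nor is the different time origin the error, since a censoring date is a calendar date. What is missing is a condition tying that date to the response.

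**Conclusion.** The concern holds in a limited form. As written, the rules can place the censoring date before the start of DOR or of duration of clinical benefit. For DOR, on the natural reading of the gap rows, they can also discard an observed progression. This is a wrong result from a stated rule, not merely a missing detail.

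The number of patients affected cannot be derived from the documents, which give no rate of first response after treatment stop or after a gap; it is probably small. Each would be about 4% of roughly 24 expected responders, assuming the Part 1 rate of 20% carries over to 122 patients. The direction of any bias in median DOR is not established. ORR and its test against 10% are unaffected.

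**What to change.** In SAP 4.2.1.1 and 4.2.2.1, state for DOR and duration of clinical benefit that:

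- the Table 4-2 gap and discontinuation rules are evaluated only from the first PR (or first MR) onward;
- a gap or treatment discontinuation before that date does not censor;
- the censoring date is never earlier than the first response date, so the minimum duration is 1 day;
- the 65-day rule still applies after response, so post-stop responders seen only every 3 months will usually be censored early;
- responders who stop treatment after first response remain censored at discontinuation, as now written.

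The last item needs saying because it treats responses just before and just after treatment stop differently. It would also help to define the discontinuation date. SAP 1.7 says the two durations are meant to follow consistent rules, so both sections should be changed together.

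The cost is a few sentences and a small derivation change. Every ORR or CBR responder then contributes a usable duration. Median DOR may move slightly.

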4.2.1.2. Analysis Methods

DOR will be summarized descriptively among those with a confirmed PR or better. Median DOR with 95% CI will be estimated based on the Kaplan-Meier method. The Kaplan-Meier curve for the duration of response will be provided.

4.2.1.3. Supportive Analyses of DOR

As supportive analyses, median DOR and 95% CI will be calculated:

- Using the BCLPD-ref, CLPD-ref, BCPD-ref, CPD-ref, all penta-ref, high-risk, EE, PP, Part 1 – Quad, Part 1 – Penta, populations respectively, if sufficient data exist
- In patients with R-ISS for MM stage I, II, and III respectively, if sufficient data exist
- In US vs. non-US patients, if sufficient data exist
- In FLC MM vs. non-FLC MM patients, if sufficient data exist.
- In patients ever received daratumumab as in combination therapy vs. as single-agent \pm dexamethasone, if sufficient data exist.
- In patients received daratumumab in last line prior treatment vs. did not receive daratumumab in last line prior treatment, if sufficient data exist.

4.2.2. Best Overall Response and Clinical Benefit Rate (CBR)

4.2.2.1. Definition

The number and percentage of patients in the individual response categories (MR, PR, VGPR, CR, sCR) based on best response will be calculated respectively.

CBR is defined as the proportion of patients who achieve a confirmed MR or better, i.e., MR, PR, VGPR, CR, sCR. Duration of clinical benefit is defined as the duration from first observation of at least MR to time of IRC-determined PD or death due to disease progression, whichever occurs first. Responders without IRC-determined PD or death due to disease progression will be censored at the censored date for TTP.

4.2.2.2. Analysis Methods

The rate of CBR and the 2-sided, exact 95% CI will be calculated using the mITT population. Median duration of clinical benefit with 95% CI will be estimated based on the Kaplan-Meier method. The Kaplan-Meier curve for the duration of clinical benefit will be provided.

As supportive analyses, CBR rate and 95% CI will be calculated:

- Using the BCLPD-ref, CLPD-ref, BCPD-ref, CPD-ref, all penta-ref, high-risk, EE, PP, Part 1 – Quad, Part 1 – Penta, doses populations respectively.
- In patients with R-ISS for MM stage I, II, and III respectively
- In US vs. non-US patients
- In FLC MM vs. non-FLC MM patients.

Median duration of clinical benefit with 95% CI will be calculated in these analysis populations and subgroups when sufficient data exist.

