### APPENDIX 3. INTERNATIONAL MYELOMA WORKING GROUP RESPONSE CRITERIA, MYELOMA

**Table 10: International Myeloma Working Group Response Criteria (Kumar 2016)**

Standard IMWG Response Criteria 	
Response Subcategory	Response Criteria
Complete response (CR)	Negative immunofixation of serum and urine, disappearance of any soft tissue plasmacytomas (SPDs), and < 5% plasma cells in bone marrow aspirates
Stringent complete response (sCR)	CR as defined above plus normal FLC ratio  and absence of clonal cells in bone marrow biopsy by immunohistochemistry ( $\kappa/\lambda$ ratio $\leq 4:1$ or $\geq 1:2$ for $\kappa$ and $\lambda$ patients, respectively, after counting $\geq 100$ plasma cells  )
Very good partial response (VGPR)	Serum and urine M-protein detectable by immunofixation but not on electrophoresis or $\geq 90\%$ reduction in serum M-protein plus urine M-protein level < 100 mg per 24 hr
Partial response (PR)	$\geq 50\%$ reduction of serum M-protein plus reduction in 24-hr urinary M-protein by $\geq 90\%$ or to < 200 mg/24 hr. If the serum and urine M-protein are not measurable, a $\geq 50\%$ decrease in the difference between involved and uninvolved FLC levels is required in place of the M-protein criteria. If serum and urine M-protein and serum FLC assay are not measurable, $\geq 50\%$ reduction in plasma cells is required in place of M-protein, provided baseline bone marrow plasma cell percentage was $\geq 30\%$ . In addition to the above criteria, if present at baseline, a $\geq 50\%$ reduction in the size (SPD) of soft tissue plasmacytomas is also required. 
Minimal response (MR)	$\geq 25\%$ but < 49% reduction of serum M-protein and reduction in 24-hr urine M-protein by 50–89%. In addition to the above criteria, if present at baseline, a $\geq 50\%$ reduction in the size (SPD) of soft tissue plasmacytomas is also required. 
Stable disease (SD)	Not recommended for use as an indicator of response; stability of disease is best described by providing the TTP estimates. Not meeting criteria for CR, VGPR, PR, MR, or PD.
Progressive disease (PD) 	Any 1 or more of the following criteria: Increase of 25% from lowest confirmed response value in 1 or more of the following criteria: Serum M-protein with absolute increase of $\geq 0.5$ g/dL;

Standard IMWG Response Criteria	
Response Subcategory	Response Criteria

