 Per IMWG, quantitative Ig levels by nephelometry may be used in place of SPEP for routine M-protein measurement for patients with IgA or IgD myeloma. Also, per IMWG, response may be confirmed if the patient fails to provide 24-hour urine sample collection after screening activities occur. See “Practical considerations for application of IMWG consensus criteria” section of the guidelines (page e340; Kumar, 2016).

 Derived from international uniform response criteria for MM ([Durie 2011](#)). MR definition and clarifications derived from Rajkumar ([Rajkumar 2011](#)). When the only method to measure disease is by serum FLC levels: CR can be defined as a normal FLC ratio of 0.26 to 1.65 in addition to the CR criteria listed previously. VGPR in such patients requires a  $\geq 90\%$  decrease in the difference between involved and uninvolved FLC levels. All response categories require 2 consecutive assessments made at any time before the institution of any new therapy; all categories also require no known evidence of progressive or new bone lesions or extramedullary plasmacytomas if radiographic studies were performed. Radiographic studies are not required to satisfy these response requirements. Bone marrow assessments do not need to be confirmed. Each category, except for SD, will be considered unconfirmed until the confirmatory test is performed. The date of the initial test is considered as the date of response for evaluation of time dependent outcomes such as DOR.

 All recommendations regarding clinical uses relating to serum FLC levels or FLC ratio are based on results obtained with the validated Freelite test (Binding Site, Birmingham, United Kingdom).

 Presence/absence of clonal cells on immunohistochemistry is based upon the  $\kappa/\lambda$  ratio. An abnormal  $\kappa/\lambda$  ratio by immunohistochemistry requires a minimum of 100 plasma cells for analysis. An abnormal ratio reflecting presence of an abnormal clone is  $\kappa/\lambda$  of  $> 4:1$  or  $< 1:2$ .

-  Plasmacytoma measurements should be taken from the CT portion of the PET/CT, or MRI scans, or dedicated CT scans where applicable. For patients with only skin involvement, skin lesions should be measured with a ruler. Measurement of tumor size will be determined by the SPD.

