2.7. SUBGROUPS

Subgroup analysis on selected efficacy endpoints will be conducted by

- R-ISS for MM (stage I, II, and III respectively)
- Region (US vs. non-US).
- FLC MM patient (yes vs. no), a FLC MM patient is defined as a patient without measurable disease in SPEP or UPEP, but with measurable disease in FLC, all based on baseline value.
- Prior daratumumab alone or in combination
 - ever received daratumumab in a combination therapy vs. as single agent ± dexamethasone

- received daratumumab in last line prior treatment (in combination therapy or as single agent ± dexamethasone) vs. did not receive daratumumab in last line prior treatment

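### Table 10 gives no free-light-chain rule for minimal response, and SAP 2.7 ignores quantitative Ig, so the FLC versus non-FLC rows for CBR and duration of clinical benefit are not like for like as written

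*SAP*

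**What the plan says.** **Response criteria (Protocol Appendix 3, Table 10).** The MR row asks for at least a 25% "but < 49% reduction of serum M-protein and reduction in 24-hr urine M-protein by 50–89"%, plus shrinkage of any plasmacytoma. It offers no FLC alternative. The PR row does: where M-protein is not measurable, a 50% "decrease in the difference between involved and uninvolved FLC levels is required in place of the M-protein criteria". The PD row has its own FLC clause. Footnote 3 deals with FLC-only patients directly: "When the only method to measure disease is by serum FLC levels: CR can be defined as a normal FLC ratio of 0.26 to 1.65", and "VGPR in such patients requires a" 90% fall in the same FLC difference. It says nothing on MR for them. A patient who fits none of CR, VGPR, PR, MR or PD is SD.

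**Eligibility (Protocol 8.4).** Criterion 3c admits patients measurable by FLC alone. Criterion 3a accepts quantitative IgA for IgA myeloma. Protocol Table 4 prefers quantitative Ig for IgA and IgD disease, applies the same percentage changes to it as to the serum M-spike, and does not allow it to be interchanged with SPEP.

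**Subgroup (SAP 2.7).** "a FLC MM patient is defined as a patient without measurable disease in SPEP or UPEP, but with measurable disease in FLC". Quantitative Ig is not mentioned.

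**Analyses.** SAP 4.2.2.1 counts MR or better as clinical benefit and starts its duration at the first MR or better. SAP 4.2.2.2 gives CBR with a 95% CI "In FLC MM vs. non-FLC MM patients", and median duration where data suffice. These rows are supportive and carry no test, although SAP section 4 lists CBR and its duration among the key secondary endpoints. SAP 4.2.7.2 (OS) and 4.2.8.2 (QoL) also group patients by MR status.

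**The concern.** If one subgroup can score MR and the other cannot, the two CBR figures measure different things: PR or better in FLC-only patients, MR or better in the rest. A lower CBR in FLC myeloma would appear even if the treatment worked equally well, and it could be read as lower activity. The planned confidence intervals would not show this, and it would not shrink with more patients.

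Duration of clinical benefit has the same problem. The clock starts at MR in one group and can start only at PR in the other, and the set of patients who contribute differs too. The direction of that distortion cannot be told in advance.

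The subgroup label adds a second fault. An IgA or IgD patient who is followed by quantitative Ig, has no measurable SPEP or UPEP disease and has measurable FLC is counted as FLC myeloma, although that patient is not followed by FLC and can score MR. This also affects the FLC comparisons of DOR (SAP 4.2.1.3) and OS (SAP 4.2.7.2).

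**Working it through.** **1. Which categories have an FLC rule in Table 10**

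| Category | FLC rule | Where |
|---|---|---|
| CR | yes | footnote 3 |
| VGPR | yes | footnote 3 |
| PR | yes | PR row |
| MR | none | MR row and footnote 3 silent |
| PD | yes | PD row |
| SD | default | SD row |

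Read as written, an FLC-only patient with a 25-49% fall is SD, so CBR = ORR for FLC-only patients.

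**2. Reproduce the plan's Part 1 figures (Protocol Table 3)**

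CBR = VGPR + PR + MR.
- All Part 1: 4 + 12 + 10 = 26; 26/78 = 33.3% (stated 33%). ORR 16/78 = 20.5%; MR 10/78 = 12.8%.
- Penta-refractory: 2 + 4 + 6 = 12; 12/30 = 40.0% (stated 40%). ORR 6/30 = 20.0%; MR 6/30 = 20.0%.

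**3. Gap between subgroups with equal true depth of response**

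Let o = ORR and m = MR rate. Gap = (o + m) - o = m.
- All Part 1 rates: 33.3% versus 20.5%, gap 12.8 points; ratio 16/26 = 0.62.
- Penta rates: 40.0% versus 20.0%, gap 20.0 points; ratio 6/12 = 0.50.

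The inputs are imprecise: exact 95% CI 6.3-22.3% for 10/78 and 7.7-38.6% for 6/30. The gap also assumes that everyone in the FLC subgroup is truly FLC-only. If only a fraction q is, because SAP 2.7 brings in patients followed by Ig, the gap is q x m.

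**4. Effect on overall CBR in Part 2**

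Shortfall = f x m, where f is the FLC-only share and N = 122 (Protocol synopsis, Study Numbers). The documents do not give f; 5-30% is an assumption. The shortfall is relative to a CBR that would allow an FLC-based MR.

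| f | FLC-only patients | m = 12.8% | m = 20.0% |
|---|---|---|---|
| 5% | 6.1 | 0.6 points (0.8 patients) | 1.0 points (1.2) |
| 10% | 12.2 | 1.3 (1.6) | 2.0 (2.4) |
| 20% | 24.4 | 2.6 (3.1) | 4.0 (4.9) |
| 30% | 36.6 | 3.8 (4.7) | 6.0 (7.3) |

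If the Part 1 MR rate was itself lowered because FLC-only patients could not score MR, the shortfall becomes f x m/(1 - f), at most 0.30 x 0.20/0.70 = 8.6 points. If f = 0 it is zero. For scale, the exact 95% CI for 49/122 (40%) is 31.4-49.4%.

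**5. What is not affected**

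ORR rests on PR or better, and PR has an FLC rule. DCR counts SD of at least 12 weeks, so most FLC-only patients who miss MR still count there.

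**The case against.** The strongest reply is that Table 10 is not the last word. The IRC assigns response under the cited IMWG criteria (SAP section 4), and that section names serum FLC among the parameters on which response may be documented. Appendix 3 sends questions of interpretation to the guideline, and procedures sit in the IRC Charter. Neither the guideline nor the charter is available here. Moreover, the MR row joins serum and urine falls with an and, so a fully literal reading would bar patients measurable in serum only. The row must be read by the parameter that applies, and the IRC may do the same for FLC.

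Most of this stands as a limit on the claim. A reader might infer that the comparison is biased by definition; the documents do not support that, because they do not show how the IRC rates these patients. A reader might also infer that overall CBR is understated. That too goes too far: under the criteria as written CBR is what was defined, and a shortfall requires FLC-only patients whose best response is a confirmed 25-49% fall, of whom no count is given.

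The reply does not close the gap. Naming serum FLC as a parameter is already needed for CR, VGPR, PR and PD, and it sets no MR threshold. The PR row spells out the FLC substitution; the MR row does not. The Part 1 MR rates also cannot settle it: the data date from 01 December 2016, before protocol version 4.1 (06 February 2017) brought in the current criteria, and whether FLC-only patients could score MR then is unknown.

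**Conclusion.** The point holds in a limited form. On Table 10 as written, FLC-only patients cannot be rated MR, so the supportive FLC versus non-FLC rows for CBR and duration of clinical benefit are not like for like unless the IRC applies a rule outside the documents. If it does not, the artificial CBR gap is about 13 to 20 points. That assumes equal depth of response, Part 1 MR rates, and a subgroup made up only of FLC-only patients. The overall CBR effect is secondary: about 0.6 to 6 points at an assumed 5-30% share, up to 8.6 under the variant, and within sampling error. These rows are descriptive, and the primary ORR analysis is untouched.

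The SAP 2.7 misclassification is a separate fault and does not depend on how the IRC rates MR. Because misclassified IgA or IgD patients can score MR, CBR need not equal ORR in the subgroup as the SAP now defines it. Correcting the plan is worthwhile because the change is cheap and the row could otherwise mislead.

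**What to change.** 1. In SAP 2.7, define FLC myeloma as measurable by FLC and not measurable by SPEP, UPEP or, for IgA and IgD disease, quantitative Ig.
2. State in the SAP, consistent with the IRC Charter, whether FLC-only patients can be rated MR and, if so, by what FLC change.
3. If they cannot:
   - drop the FLC versus non-FLC rows for CBR and duration of clinical benefit, or footnote that CBR equals ORR for FLC-only patients;
   - keep the PR-or-better endpoints for that comparison;
   - report CBR excluding FLC-only patients as a sensitivity analysis, with the number excluded;
   - footnote the OS and QoL analyses by MR status (SAP 4.2.7.2 and 4.2.8.2) in the same way.

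The cost is SAP wording, a check against the charter, and a CBR subgroup comparison (with its duration) lost or qualified. No new data are needed.
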